#### **3.4.2. Change in Total Contusion Volume (hematoma plus perihematomal edema) from Baseline to 24 Hours**

Change in total contusion volume (hematoma plus perihematomal edema) as measured by brain imaging from baseline to 24 hours or prior to DC, IPH evacuation, or CMO if these procedures occur before 24 hours per central review, will be derived from available central reads, at baseline (before Hour 0) and closest to Hour 24. If multiple timepoints are applicable, the read closest to Hour 24 will be used for analysis.

#### **3.4.3. Change in Absolute Hematoma Volume from Baseline to 24 Hours**

Change in absolute hematoma volume from baseline to 24 hours will be derived from available central reads, at baseline (before Hour 0) and closest to Hour 24. If multiple timepoints are applicable, the read closest to Hour 24 will be used for analysis.

#### **3.4.4. Change in Absolute Edema Volume from Baseline to 96 Hours**

Change in absolute edema volume from baseline to 96 hours will be based on the edema volume measurements from the same follow-up visit for evaluating the total contusion volume.

### **3.5. Stratification Factors and Subgroup Variables**

#### **3.5.1. Stratification Factors**

The randomization will be stratified by the follow risk factors:

- Baseline contusion volume per investigator assessment of NCCT scan or site local radiologic assessment
  - > 3 to 10 mL
  - > 10 mL
- Baseline Glasgow Coma Scale (GCS)
  - 5 to 8
  - 9 to 12
  - 13 to 15
- Age
  - $\leq$  70 years old
  - > 70 years old
- Region
  - North America (United States)

- Rest of World (RoW)

### 3.5.2. Subgroup Variables

Subgroup variables will include stratification factors per IRT as described in Section [3.5.1](#) and following subgroup variables per Case Report Forms (CRFs):

- Age category at screening ( $\leq 70$ ;  $> 70$  years)
- Sex (Female; Male)
- Race category (White; Non-White)
- Ethnicity (Hispanic/Latino; Not Hispanic/Latino)
- Baseline brain contusion volume per investigator ( $\leq 10$ ;  $> 10$  mL)
- Baseline brain contusion volume per the central review ( $\leq 10$ ;  $> 10$  mL)
- Baseline hematoma volume per central review ( $\leq$  median;  $>$  median)
- Baseline edema volume per central review ( $\leq$  median;  $>$  median)
- Baseline Glasgow Coma Scale (GCS: 5 to 8; 9 to 12; 13 to 15)
- Baseline blood glucose ( $\leq$  median;  $>$  median)
- Baseline alcohol level ( $\leq$  median;  $>$  median)
- Baseline sodium ( $\leq$  median;  $>$  median)

By median in the above subgroup definitions is referred to the median of available measures of the variable in all treatment groups combined.

## 3.6. Analysis Sets

The analysis sets include the full analysis set (the modified intention-to-treat participants), per-protocol analysis set, and the safety analysis set. All participants who have signed the informed consent form will be used for the enrollment summary. All randomized participants following the intention-to-treat principle will be used for time-to-event analysis (including the participants who are randomized but do not receive any study drug).

### 3.6.1. Full Analysis Set

The full analysis set, i.e., the modified intention-to-treat (mITT) participants, will include all the participants who are randomized, receive any study drug (BIIB093 3 mg/day, BIIB093 5 mg/day or the matching placebo), and have at least one final read per central review of contusion volume from an NCCT or MRI scan acquired between 10 hours after the initiation of study drug infusion and the Hour 96 visit or NSx or CMO (if earlier). In efficacy analyses performed on the full analysis set (mITT participants), participants will be analyzed according to the randomized treatment group (see [Section 3.2.1](#) for the definition).

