4.2. Current Therapies for Brain Contusion

Brain contusion is a devastating public health problem with no approved pharmacologic treatment to stop or slow the progression of lesions following the initial trauma. The standard of care remains primarily supportive, with the maintenance of hemostasis to limit ongoing bleeding, and with surgical evacuation or other means to reduce intracranial pressure (i.e., insertion of ventricular drains, osmotherapy, or decompressive craniectomy [DC]) [Carney 2016; Haddad and Arabi 2012]. Despite these interventions, brain contusions may continue to progress, particularly during the first 12 hours following a TBI. There is no standard of care to limit HPC, leaving an urgent unmet medical need. Studies of hemostatic agents, including recombinant factor 7 and tranexamic acid, have yielded mixed results and are not routinely used in clinical practice.

CONFIDENTIAL

The information contained herein may not be used, disclosed, or published without the written consent of Biogen MA Inc.

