AE = adverse event; BG = blood glucose; CMO = comfort measures only; d = days; DC = decompressive craniectomy; ECG = electrocardiogram; eCRF = electronic case report form; ET = early termination; [REDACTED]; GCS = Glasgow Coma Scale; GOS-E = Glasgow Coma Scale-Extended; h = hours; INR = international normalized ratio; IPH = intraparenchymal hematoma; LFT = liver function test; LKN = last known normal; MRI = magnetic resonance imaging; mRS = modified Rankin Scale; NCCT = noncontrast computed tomography; NSx = neurosurgical intervention; [REDACTED] PTT = partial thromboplastin time; [REDACTED]; SAE = serious adverse event; SOC = standard of care; TT = time of trauma.

CONFIDENTIAL

The information contained herein may not be used, disclosed, or published without the written consent of Biogen MA Inc.

¹ Hour 0 is defined as the start of study treatment infusion.

² In the event a participant is discharged from the hospital prior to Hour 96, every effort should be made to obtain neuroimaging (NCCT or MRI) prior to discharge.

³ If a participant is due to be discharged from hospital prior to Day 7, every effort should be made to perform the Day 7 assessments at the time of discharge or just prior.

⁴ All visits after hospital discharge can be conducted by telephone; however, the Day 90 and Day 180 Visits should be in person whenever possible. Should the follow-up visits at Day 90 and Day 180 be conducted remotely, [REDACTED].

⁵ Scans (NCCT or MRI) obtained within 12 hours of IPH evacuation, DC, or CMO meet the requirement. Scans are not expected for other NSx interventions. If IPH evacuation, DC, or CMO are indicated prior to 96 hours, an NCCT or MRI scan in the 12 hours proceeding the procedure should be collected, and no further post procedural images are required beyond SOC.

⁶ NCCT as SOC at Screening (prior to enrollment). If not eligible per SOC scan, a single, repeat, study-specific NCCT may be obtained to reassess contusion volume if feasible within the protocol-specified time window.

⁷ Optional Hour 96 NCCT should be obtained in addition to the MRI whenever possible, after study treatment infusion is complete, within 18 hours of the Hour 96 timepoint.

⁸ Only performed if participant has not yet been discharged from hospital.

⁹ Vital signs include temperature, pulse rate, systolic and diastolic blood pressure, respiratory rate, and oxygen saturation. Measurements taken nearest to the assessment timepoint should be recorded.

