12.2. Placebo

Placebo vials are to be stored at 1°C to ≤ 25°C (34°F to ≤ 77°F) and protected from light in a secured location with limited access. Each vial of matching placebo contains mannitol 180 mg, as well as sufficient sodium hydroxide to adjust pH during manufacture. The pH of the infusion is approximately 6 to 8.

CONFIDENTIAL

The information contained herein may not be used, disclosed, or published without the written consent of Biogen MA Inc.

13. **EFFICACY, [REDACTED] PHARMACOGENETIC, AND GENETIC ASSESSMENTS**

See Section 5 for the timing of all assessments.

13.1. **Clinical Efficacy Assessments**

NOTE: the 90- and 180-Day efficacy outcomes will be performed by personnel who are blinded to on-treatment BG levels, BG-related AEs, and carbohydrate administration (e.g., intravenous glucose or parenteral nutrition). Such persons will not have access to the participant's medical record from the acute hospitalization study period but will instead be provided with participant/family/LAR contact details (if they are required to schedule the follow-up), the source documents for the assessments to be performed, and the list of unresolved AEs for the 30-, 90-, and 180-day follow ups.

The following clinical and imaging assessments will be performed to evaluate the efficacy of BIIB093:

- NCCT/MRI Assessments
 - Total contusion volume will be assessed by the central imaging core laboratory on baseline NCCT, 24-hour NCCT, and the 96-hour scan (MRI and/ or NCCT) and the scans obtained prior to DC, IPH evacuation, or CMO.
 - Absolute hematoma volume from baseline to 24 hours (the NCCT scan closest to the 24-hour timepoint will be used) unless DC, IPH evacuation, or CMO occurred prior to 24 hours, the scan acquired just prior to these procedures will be used.
 - Absolute edema volume from baseline to 96 hours (the MRI and/or NCCT scan closest to the 96-hour timepoint will be used) unless DC, IPH evacuation, or CMO occurred prior to 96 hours, in which case the scan acquired just prior to these procedures will be used.
- [REDACTED]
- NCCT and MRI will be acquired per specifications outlined in the Imaging Manual.
- All imaging reads for efficacy will be performed by trained and certified central readers blinded to treatment assignment per procedures detailed in the Imaging Manual.
- Functional/Neurological Outcomes Assessments

CONFIDENTIAL

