16.2. Efficacy

16.2.1. Analysis Population

The primary efficacy analyses will be conducted in the modified intent-to-treat population, which is defined as participants who are randomized and treated and have at least 1 centralized read of contusion volume from an NCCT or MRI scan acquired between 12 hours after the initiation of study treatment and by the Hour 96 Visit or prior to DC, IPH evacuation, or CMO, if performed before the Hour 96 visit.

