16.2.2.3. Analysis of the Secondary Endpoints

GOS-E at Day 180

GOS-E at Day 180 will be analyzed as a 7-category ordinal scale (1/2, 3, 4, 5, 6, 7, and 8) using ordinal logistic regression, adjusting for covariates including all the stratification factors at randomization and baseline contusion volume per the central review and baseline GCS. Multiple imputation will be used to account for missing GOS-E at Day 180.

mRS at Day 90

mRS at Day 90 will be analyzed as a 5-category ordinal scale (0/1, 2, 3, 4, and 5/6) using ordinal logistic regression, adjusting for covariates including all the stratification factors at randomization, baseline contusion volume per the central review, and baseline GCS.

Proportion of participants requiring delayed intubation

The proportion of participants requiring delayed intubation at any time between 24 hours and 96 hours post injury or LKN will be analyzed at Day 4. The analysis will compare BIIB093 (3 mg/day or 5 mg/day) and placebo groups using a binary logistic regression, adjusting for covariates including all the stratification factors at randomization and baseline contusion volume per the central review and baseline GCS.

Change in total contusion volume (hematoma plus perihematomal edema) from baseline to 24 hours

An ANCOVA model will be used to compare BIIB093 (3 mg/day or 5 mg/day) and placebo groups, adjusting for covariates including all the stratification factors at randomization, and baseline contusion volume per the central read. This endpoint will be evaluated for all participants having a scan acquired between 12 hours after the initiation of study treatment and the end of the Hour 24 Visit. Summary statistics, including by-visit number of participants with data, mean, SD, median, quartiles, and range will be provided.

CONFIDENTIAL

The information contained herein may not be used, disclosed, or published without the written consent of
Biogen MA Inc.

Change in absolute hematoma volume from baseline to 24 hours

Analysis of covariance (ANCOVA) will be performed to compare the mean change from baseline between BIIB093 (3 mg/day or 5 mg/day combined) and placebo groups. This endpoint will be evaluated for all participants having a scan acquired between 12 hours after the initiation of study treatment and the end of the Hour 24 Visit. Summary statistics, including by-visit number of participants with data, mean, SD, median, quartiles, and range will be provided.

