### 5.6.2. Primary Efficacy Endpoint

Primary endpoint is the change in total contusion volume (hematoma plus perihematomal edema) as measured by brain imaging from baseline to 96 hours or prior to DC, IPH evacuation or CMO if these procedures occur before 96 hours per the central review. The definition of main estimand follows a white-on-treatment strategy [ICH E9 (R1) Addendum, 2020], i.e., all the central reads between 12 hours after the initiation of study drug infusion and Hour 96 or prior to DC, IPH evacuation or CMO if these procedures occur before 96 hours will be used; see details in Section [3.4.1](#).

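### The 10 or 12 hour post-dose floor on admissible scans overrides the pre-procedure scan that the endpoint definitions say is used, so some treated participants leave the mITT set because of an early procedure

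*SAP*

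**What the plan says.** **Endpoint.** Protocol 6 and SAP 3.4.1 define the primary endpoint as the volume change to 96 hours, or to the scan before DC, IPH evacuation or CMO if one of these comes first. SAP 3.4.2 does the same for the 24-hour change. None of them sets a minimum time after dosing. Protocol 13.1 says of the 24-hour hematoma volume: "unless DC, IPH evacuation, or CMO occurred prior to 24 hours, the scan acquired just prior to these procedures will be used".

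**Scan collection.** Protocol 5, Table 2, footnote 5: "Scans (NCCT or MRI) obtained within 12 hours of IPH evacuation, DC, or CMO meet the requirement". The same footnote asks for no study imaging after the procedure.

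**Analysis set and admissible reads.**
- SAP 3.6.1 asks for imaging "acquired between 10 hours after the initiation of study drug infusion and the Hour 96 visit or NSx or CMO (if earlier").
- Protocol 16.2.1 asks for imaging "acquired between 12 hours after the initiation of study treatment and by the Hour 96 Visit or prior to DC, IPH evacuation, or CMO".
- SAP 5.6.2, in its main estimand, uses "all the central reads between 12 hours after the initiation of study drug infusion and Hour 96", followed by a mention of reads before the three procedures.
- Protocol 16.2.2.3, 24-hour endpoints: "all participants having a scan acquired between 12 hours after the initiation of study treatment and the end of the Hour 24 Visit".
- SAP Table 1: the Hour 24 volume window opens at 10 hours.

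**Images read.** SAP Appendix 1 sends every image up to the Hour 96 visit, or to NSx or CMO if earlier, to central review. It has no lower time limit.

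**The concern.** The endpoint definition and the analysis set disagree about the same participants. The endpoint was written so that someone who has DC, IPH evacuation or CMO still contributes the last scan before it. The analysis set then discards that scan if it was taken too soon after dosing, and removes the participant with it.

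Removal depends on something that happens after randomization and is related to the outcome, since expansion is one reason for surgery or for a change to comfort care. It also reaches beyond imaging. SAP 5.6 and Table 3 place GOS-E at Day 180, mRS at Day 90 and delayed intubation in the same mITT set, and SAP 5.1.4 imputes GOS-E for mITT participants only. Someone with DC at Hour 8 would therefore be missing from functional analyses that need no scan.

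Sections also differ on whether the floor is 10 or 12 hours. That needs reconciling too, but it is a separate matter: any floor has this effect on pre-procedure scans.

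**Working it through.** **1. Timing.** Let F be the floor and T the procedure time, in hours after infusion start.
- T below F: the admissible window would run from F to T, so it is empty. With DC at Hour 8 and a scan at Hour 7, the endpoint definition uses the scan and SAP 3.6.1 removes the participant.
- T above F: footnote 5 accepts a scan from T − 12 to T. Part of that range is below F while T − 12 < F, that is, T < F + 12. This gives Hour 22 for F = 10 and Hour 24 for F = 12.
- Share of the accepted range below the floor, (F − (T − 12))/12:

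| Procedure at | F = 10 | F = 12 |
|---|---|---|
| Hour 14 | 8/12 = 67% | 10/12 = 83% |
| Hour 18 | 4/12 = 33% | 6/12 = 50% |
| Hour 24 | 0% | 0% |

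Example: IPH evacuation at Hour 20 with the only scan at Hour 9 satisfies footnote 5 and leaves no admissible read.

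**2. Does anything restore these participants?**
- Later scans: not required by footnote 5, and not on-protocol under SAP 3.4 and Appendix 1.
- Imputation: Protocol 16.2.2.2 imputes missing Hour 96 values, but within a set that already requires an admissible scan. SAP 5.6.2 specifies none for the primary endpoint.
- Other analyses: one supplementary analysis in SAP 5.6.2 removes procedure cases, and the per-protocol set is a subset of mITT. Neither adds early cases back.
- Survival: SAP 3.6 and 5.6.3 analyze it in all randomized participants, so they remain there.

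**3. The plan's own power figure.** Inputs from Protocol 16.8: 80 vs 80, difference 15 mL, SD 29 mL, two-sided 5%. SE = 29 × √(2/80) = 4.6 mL. Power ≈ Φ(15/4.585 − 1.96) = Φ(1.31) = 0.905, or 0.902 with the noncentral t. The stated 90% reproduces and is not in dispute. It takes all 160 randomized as analyzed.

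**4. Range under assumed losses.** The documents give no early-procedure rate, so every loss rate and volume below is an assumption, apart from the plan's 15 mL and SD of 29 mL.
- Equal loss of 5% per arm (76 vs 76) gives t-test power 0.886; 10% (72 vs 72) gives 0.869.
- Unequal loss: suppose the true difference is 15 mL and lost participants expand D mL more than retained ones in their arm. The retained difference is 15 − D × (f_placebo − f_active). With D = 29 and losses of 10% placebo, 5% active: 15 − 29 × 0.05 = 13.6 mL. With the losses reversed: 15 + 1.45 = 16.5 mL.
- Restoring early scans: suppose retained means of 28 mL (placebo) and 15 mL (active), a difference of 13.0 mL, with 8 placebo and 3 active participants restored, each showing x mL. The estimate is (72 × 28 + 8x)/80 − (77 × 15 + 3x)/80 = (861 + 5x)/80. At x = 45 it is 13.6 mL; at x = 10 it is 11.4 mL; it stays at 13.0 mL when x = 35.8. With 4 and 1 restored, (943 + 3x)/80 stays at 13.0 mL when x = 32.3.

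The sign depends on which arm has more early procedures and on how far the contusion has grown by the early scan. The documents give neither.

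**The case against.** **The group is probably small.** Exclusions 1 to 3 and 30 (Protocol 8.2) keep out people expected to have care withdrawn within 24 hours, those with an immediate indication for IPH evacuation or DC, those with herniation signs, and those likely to move to CMO at 24 to 96 hours. This stands. It does not cover unforeseen deterioration after enrollment.

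**Hour 22 to 24 is a worst case.** Standard-of-care scans also go to the core laboratory (Protocol 19.1.5), and any scan between the floor and the procedure admits the participant. This stands for procedures after the floor. It does not help when the procedure precedes the floor.

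**The floor was deliberate.** The Version 2 amendment rationale shows that a 12 hour minimum was intended, and a minimum post-dose interval is defensible. But it was written for the earlier binary expansion endpoint and does not resolve the conflict with the current definition.

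**The wording might already exempt these scans.** Protocol 16.2.1 and SAP 5.6.2 could be read as giving pre-procedure scans a separate route without a floor. The qualifier that ends the window in SAP 3.6.1 leaves little room for that. If it was intended, the fix only states it.

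**A stronger reading that does not hold.** A reader might infer that the floor removes the fastest expanders, mostly on placebo, and so biases the estimate by a known amount. Protocol 4.2 says "brain contusions may continue to progress, particularly during the first 12 hours following a TBI", but that clock starts at injury. The floor starts at dosing, which may be up to 10 hours later. For someone dosed 8 to 10 hours after injury, those 12 hours end at Hour 4 to Hour 2. CMO may also have causes other than expansion. In the scenario above, restoring early scans can narrow the difference as easily as widen it, and a shift from 13.0 to 13.6 mL is only 0.6/4.6 = 0.13 SE.

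**Conclusion.** The conflict is real and follows from the text. Pre-procedure scans are the endpoint scans by definition, but are inadmissible if taken before 10 or 12 hours after infusion start. Treated participants with a procedure before the floor, and at worst up to about Hour 22 to 24, leave the mITT set and its functional analyses on the basis of a post-randomization event related to the outcome. No planned analysis restores them.

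The number is not given and is probably small. The direction and size of any bias cannot be derived from the documents, so the ranges above are illustrations, not estimates. The case for change is that the analysis set should match the plan's own endpoint, at low cost, using scans already sent for central reading.

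**What to change.** 1. In SAP 3.6.1, 5.6.2 and Table 1 (Hour 24 volume row), and in Protocol 16.2.1 and 16.2.2.3, state that the lower time limit does not apply to the last scan after Hour 0 and before DC, IPH evacuation or CMO. That scan is the endpoint scan whatever its time.
2. In SAP 3.4, 3.6.1 and Appendix 1, replace NSx with DC or IPH evacuation, as in the endpoint. Protocol 11.4.2.1 also covers extra-axial evacuation and ventricular drains under neurosurgical intervention. Left as it is, the NSx cutoff could still remove participants after early surgery that the endpoint does not count.
3. Keep treated participants with no post-dose, pre-procedure read in the set. Carry the multiple imputation of Protocol 16.2.2.2 into the SAP for their primary value, and say which value is imputed. Analyze their functional endpoints as observed or imputed.
4. Report by arm how many participants had only a pre-floor scan, and add a sensitivity analysis that applies the floor.

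**Cost.** SAP wording, one derivation rule, the imputation text and a matching protocol edit, which goes to the ethics committee under Protocol 19.3. No new scans are needed. The downside is that a few very early scans enter the primary endpoint and cut off later edema growth, which Protocol 4.5.1.3 says can occur as late as 3 to 4 days after injury. The sensitivity analysis in item 4 shows how much that matters.

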## 6. Changes from Protocol-Specified Analyses

Not applicable for this version.

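### The SAP admits participants to the primary analysis set on a scan from 10 h after the start of infusion, but the SAP's primary estimand and the protocol's mITT definition both start at 12 h, and no change is declared

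*SAP*

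**What the plan says.** Four places bear on the primary analysis.

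- SAP 3.6.1 (Full Analysis Set) requires at least one final central read of contusion volume on a scan taken "between 10 hours after the initiation of study drug infusion and the Hour 96 visit or NSx or CMO (if earlier").
- SAP 5.6.2 (Primary Efficacy Endpoint) defines the main estimand by "all the central reads between 12 hours after the initiation of study drug infusion and Hour 96", ending sooner where decompressive craniectomy, hematoma evacuation or comfort care comes first, and refers to SAP 3.4.1 for details.
- Protocol 16.2.1 (Analysis Population) defines the modified intent-to-treat population by a "scan acquired between 12 hours after the initiation of study treatment and by the Hour 96 Visit", ending sooner in the same circumstances.
- SAP Section 6 (Changes from Protocol-Specified Analyses) reads "Not applicable for this version".

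For the two 24-hour volume endpoints (total contusion and hematoma), protocol 16.2.2.3 evaluates participants "having a scan acquired between 12 hours after the initiation of study treatment and the end of the Hour 24 Visit". SAP Table 1 sets the Hour 24 volume window at [10, 38] h and the Hour 96 volume window at [76, 116] h.

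**The concern.** One rule decides who is in the primary set and another decides which reads may be used for them, and the two rules start 2 h apart. A participant can be counted in the primary set on the strength of a scan that the estimand then excludes. The SAP does not say whether that participant's primary value is the early read, an imputed value, or nothing.

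The same lower limit sets the denominator beyond the primary endpoint. Under SAP 5.6, efficacy endpoints use the mITT participants unless otherwise specified, which brings in GOS-E, mRS and delayed intubation. SAP 4.1 also uses the mITT population for the interim analysis.

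What is at stake is selection and reproducibility more than precision. The scheduled Hour 24 scan is due at 24 ± 6 h, so a sole scan at 10 to 12 h comes from an unscheduled scan, an early discharge, or a scan before an early procedure or comfort care. Participants who deteriorate early are the ones the endpoint's pre-procedure rule is written to capture. If the limit is settled after unblinded results have been seen, the choice could look data-driven.

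**Working it through.** **Plan's own figure.** The inputs from SAP 2.3 and protocol 16.8 are a difference of 15 mL, SD 29 mL, 80 per pooled group and two-sided alpha 0.05. With the normal approximation, power = Φ(δ / (σ√(2/n)) − 1.96):

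- σ√(2/n) = 29 × √(2/80) = 4.585
- 15 / 4.585 = 3.271
- Φ(3.271 − 1.96) = 0.905

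The two-sample t-test gives 0.902. The stated figure of about 90% reproduces.

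**The rules side by side**, for a treated participant classified by the time of the only post-dose scan, taken before any procedure:

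| Only post-dose scan | SAP 3.6.1 set | Protocol 16.2.1 set | Read admitted by SAP 5.6.2 |
|---|---|---|---|
| Before 10 h | out | out | no |
| 10 to 12 h | in | out | no |
| 12 h to the Hour 96 visit | in | in | yes |

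Only the middle row conflicts, and it conflicts both within the SAP and between the SAP and the protocol.

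**Can the middle row occur?** Footnote 5 of protocol Table 2 accepts a scan taken within 12 h of hematoma evacuation, decompressive craniectomy or comfort care, and requires no further study imaging afterwards. As an illustration, take a procedure at 14 h with its scan at 11 h. The gap is 14 − 11 = 3 h, which meets the footnote, and the 11 h scan may be the last one.

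**Effect on power.** The number in the middle row is not given, so the losses below are assumed and split evenly between the pooled groups:

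| Participants leaving the set | Per group | t-test power |
|---|---|---|
| 0 | 80 | 0.902 |
| 2 | 79 | 0.898 |
| 4 | 78 | 0.894 |
| 8 | 76 | 0.886 |
| 16 | 72 | 0.869 |

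**24-hour endpoints.** The SAP window opens 12 − 10 = 2 h before the protocol's. SAP 3.1 takes the scan closest to target. A scan at 11 h is 13 h from target and an on-schedule scan is at most 6 h away, so anyone with an on-schedule scan contributes that scan under either rule. Only participants with no on-schedule scan can differ.

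**The case against.** The best defence is that set membership is defined once in the SAP, in 3.6.1. SAP 5.6.2 says which reads enter the estimand, not who is in the set. Protocol Section 16 leaves the final statistical details to the SAP, so programmers working from the SAP would build the same mITT set. This stands, and a reader should not infer that the SAP contains two definitions of its primary set. It does not remove the conflict: the SAP's set and its reads still do not match, and the set differs from the protocol's without being declared.

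The defence can add that SAP 3.4.1, to which 5.6.2 defers, has no lower limit and takes the read closest to Hour 96 or the pre-procedure scan. On that text a read at 11 h is arguably usable. That makes its status uncertain, since 5.6.2 itself says 12 h.

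Four stronger readings are tempting, and the documents do not support them.

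- That Table 1 sets a 10 h limit for primary reads. Its [10, 38] window belongs to Hour 24; the Hour 96 window starts at 76 h.
- That the current protocol limits primary reads to 12 h. In 16.2.1 the 12 h governs population membership, and 16.2.2.2 gives no lower limit for reads. The protocol file ties 12 h to primary reads only in its summary of superseded Version 2 changes.
- That the 24-hour endpoints suffer more because the SAP window is 38 − 10 = 28 h wide against 30 − 12 = 18 h in the protocol. Width is not a count of people. The 30 h is inferred from the ± 6 h visit tolerance and is not stated in 16.2.2.3.
- That lacking an Hour 96 value is peculiar to this band. A participant with only a 24 h scan is in the mITT set under either limit. The protocol plans multiple imputation for Hour 96 and the SAP's primary-endpoint section describes none. That question is separate, and aligning the limits does not answer it.

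**Conclusion.** The point holds in a narrow form: 10 h in SAP 3.6.1 disagrees with 12 h in SAP 5.6.2 and in protocol 16.2.1, and SAP Section 6 does not declare the difference. As written, following both SAP rules puts a participant whose only scan is at 10 to 12 h in the primary set with a read that 5.6.2 excludes.

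The size is probably small. That rests on the scan schedule, not on a count, because the documents give no number. Even an assumed loss of 16 of 160 leaves power near 0.87. The remaining risk is bias: scans this early with none later may come disproportionately from participants heading to early surgery or comfort care. The documents give neither the direction nor the amount of any such bias.

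For the 24-hour endpoints the same undeclared 2 h difference exists at the lower end. The 38 h upper end also needs declaring if it is meant to depart from the protocol. It is not an error in itself, since analysis windows wider than visit tolerances are ordinary.

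**What to change.** Before the Day 4 database lock and before any unblinded look, including the interim analysis:

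1. Use 12 h in SAP 3.6.1, which then agrees with SAP 5.6.2 and protocol 16.2.1. If 10 h is intended, change 5.6.2 to 10 h, so that reads at 10 to 12 h are admitted to the primary endpoint, and declare the change with its reason in SAP Section 6.
2. Start the Hour 24 volume window in SAP Table 1 at 12 h, or declare [10, 38] in Section 6 as a deliberate departure from protocol 16.2.2.3. The upper limit need not be cut to 30 h; doing so would discard off-schedule scans.

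If 10 h is kept, a sensitivity analysis with the 12 h limit would show whether the choice matters. The cost is a few lines of SAP wording. Planned sample size and data collection do not change.
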